#### 3.3.4.2 Discontinuation of the trial by the sponsor

Boehringer Ingelheim reserves the right to discontinue the trial overall or at a particular trial site at any time for the following reasons:

1. Failure to meet expected enrolment goals overall or at a particular trial site
2. Emergence of any efficacy/safety information invalidating the earlier positive benefit-risk-assessment that could significantly affect the continuation of the trial
3. Violation of good clinical practice (GCP), the clinical trial protocol (CTP), or the contract disturbing the appropriate conduct of the trial

The Investigator / the trial site will be reimbursed for reasonable expenses incurred in case of trial termination (except in case of the third reason).

## 4. TREATMENTS

### 4.1 TREATMENTS TO BE ADMINISTERED

Patients will be randomised 1:2 to 300 mg nintedanib daily (i.e. one capsule of nintedanib 150 mg in the morning and one capsule of nintedanib 150 mg in the evening) or matching placebo (i.e. one capsule of matching placebo in the morning and one in the evening) during the first 12 weeks of the treatment period. For the subsequent 40 weeks all randomised patients will enter the single active arm treatment. All patients previously receiving placebo will start taking nintedanib.

During the trial, permanent or intermittent dose reduction to a total daily dose of nintedanib 200 mg, i.e. 100 mg bid and intermittent drug interruptions are allowed to manage AEs as described in [Section 4.2.1](#). Re-escalation to nintedanib 150 mg bid is also allowed as described in [Section 4.2.1](#).

Trial medication will be provided as a medication kit. One medication kit will contain seven blister cards each containing 10 soft gelatin capsules of either blinded nintedanib 150 mg, or blinded nintedanib 100 mg, or matching placebo (for blinded part of the trial) and open label nintedanib 150 mg, or open label nintedanib 100 mg (for the open label part) thus allowing sufficient amount of medication for approximately one month. Sufficient amount of kits, each identified with a unique medication number, will be dispensed to each patient throughout the trial via IRT. No active comparator is used in this trial.

Trial medication is manufactured by Boehringer Ingelheim.

#### 4.1.1 Identity of BI investigational product(s) and comparator product(s)

Table 4.1.1: 1 Nintedanib:

Substance:	Nintedanib (Ofev ® )
Pharmaceutical formulation:	Soft gelatin capsule
Source:	BI Pharma GmbH & Co. KG
Unit strength:	150 mg, 100mg
Posology	1 capsule, bid
Route of administration:	Oral (swallowed)

Table 4.1.1: 2 Placebo matching Nintedanib

Substance:	N/A
Pharmaceutical formulation:	Soft gelatin capsule
Source:	BI Pharma GmbH & Co. KG
Unit strength:	N/A
Posology	1 capsule, bid
Route of administration:	Oral (swallowed)

#### **4.1.2 Method of assigning patients to treatment groups**

To guarantee the double-blind design of the study, all treatments will be indistinguishable for the patient as well as for the investigator.

After final assessment of all inclusion and exclusion criteria, each eligible patient will be randomly assigned in 1:2 ratio (treatment: placebo) to one of the two treatment options at Visit 2 (double blind phase applicable to the first 12 weeks only). An interactive voice response system (IRT) will be used for randomisation to a specific treatment group in this trial and for the appropriate supply and re-supply of study medication to patients throughout the trial. Patients will be randomised to receive either an active drug at a dosage of 150 mg bid or matching placebo.

Documents such as but not limited to user guides, instructions, worksheets on the IRT will be stored in the ISF.

Note that the medication number is different from the patient number (the latter one is assigned after the informed consent process has been completed).

#### 4.1.3 Selection of doses in the trial

A dose of nintedanib 150 mg bid (total daily dose of 300 mg) was selected for this trial as this is the recommended dose based on prescribing information in participating countries as well as the dose that has shown to be efficacious in two replicate phase III trials.

Dose adjustments are permitted as per [Section 4.2](#).

#### 4.1.4 Drug assignment and administration of doses for each patient

##### Drug assignment

Dosage for an individual patient will be assigned by means of an IRT at Visit 2. Patients will be randomised to receive either an active drug at a dosage of 150 mg bid or matching placebo.

At Visit 5, all patients will start receiving open label nintedanib for the remainder of the trial. Patients previously receiving placebo will now start receiving nintedanib. All patients will remain on the same dose they were previously receiving unless prescribed otherwise by the investigator. Patients, site staff and trial team will remain blinded to patient's previously randomised treatment group.

Study treatment will comprise of 1 capsule twice daily throughout the trial (refer to [Section 4.1](#)). Treatment kits containing 4 weeks + 1 week reserve treatment (one treatment kit containing 7 blister cards each having 10 capsules) will be dispensed to the patients.

To ensure patients receive adequate supply of study medication, kits will be dispensed at clinic visits in quantities outlined in [Table 4.1.4: 1](#). Unscheduled re-supplies with additional medication kits will be possible via the IRT.

Table 4.1.4: 1 Quantity of medication kits dispensed

Visit	Week	Number of medication kits
2	0	1*
3	4	1*
4	8	1*
5	12	3**
8	24	3**
9	36	4**

\* Double-blind study drug

\*\*Open label active treatment study drug

The investigational product should only be dispensed to participating patients according to the protocol by authorised personnel as documented on the Investigator's Trial Staff List. All unused medication must be returned to the Sponsor. Receipt, usage and return must be documented on the respective forms. Any discrepancies must be accounted for.

#### Drug administration

- Study drug will be administered orally on a twice daily basis (bid). **At all clinic visits the study drug will be administered at the study site (after any sampling procedures and PFTs).** The patients should swallow the study medication unchewed together with a glass of water (~250 mL), and should observe a dose interval of approximately 12 hours. Study drug needs to be taken at approximately the same time every day (preferably between 06:00 and 11:00 in the morning, and between 18:00 and 23:00 in the evening).
- Because nintedanib may cause stomach discomfort, it is recommended to take the administered drug after the meal.
- If a dose of nintedanib is missed, i.e. not taken between 06:00 and 11:00 in the morning, and between 18:00 and 23:00 in the evening, administration should resume at the next scheduled time at the recommended dose. No catch up of missed doses is permitted.

Patients experiencing adverse effects requiring temporary drug discontinuation (refer to [Section 4.2.1](#) and [4.2.2](#)) may start to receive study drug at 100 mg bid. The dose can also be reduced without prior discontinuation, i.e. immediately stepping down from 150 mg bid to 100 mg bid if necessary. In the case of severe toxicity or when the reduced dose is again not tolerated, drug treatment must be stopped and cannot be restarted. All dose reductions must be approved by the Investigator or delegated site staff at the site (during the scheduled or unscheduled visit) and the reason for reduction must be documented.

In case of adverse events requiring dose reduction (refer to [Sections 4.2.1](#) and [4.2.2](#)), 100 mg bid (or matching placebo) will be assigned by IRT upon call of the Investigator. The colour of the 150 mg capsules and the 100 mg capsules will be slightly different; the packaging will remain the same (same number of capsules per blister, same number of blisters per box).

If the reduced dose is well tolerated, re-escalation to 150 mg bid is possible, according to procedures described in [Section 4.2.1.1](#).

The amount of study drug dispensed at the time of dose reduction and dose re-escalation is dependent upon the amount of time between the unscheduled visit and the next planned study visit. Therefore at unscheduled visits for dose reductions and dose re-escalations, IRT will assign only the number of boxes of study medication needed until the next predicted planned patient visit as noted within the IRT system.

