#### **4.2.1.1 Recommendations for managing adverse events (exceptions include diarrhea and liver enzyme elevations)**

- If a patient experiences adverse events considered related to the trial medication, symptomatic treatment should be initiated (e.g. anti-emetic treatment such as dimenhydrinat if appropriate).
- Patients experiencing adverse events considered related to nintedanib may require drug interruption or reduction of dose (at the discretion of the investigator) to allow for resolution of symptoms.
- After resolution of AE, nintedanib may be reintroduced and re-escalated to the higher dose (at the discretion of the investigator):

- If dose has been reduced, consider re-escalation to 150 mg bid
- If treatment was temporarily interrupted, resume treatment at the full dose (150 mg bid), or at the reduced dose (100 mg bid), which subsequently may be re-escalated to the full dose (150 mg bid).
- For adverse events not related to the trial medications, treatment interruptions are allowed. Nintedanib should then be resumed at the same dose taken prior to interruption.
- In the occurrence of acute IPF exacerbations all treatment options considered adequate by the investigator are allowed, except concomitant treatment with pirfenidone.

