#### 4.2.1.2 Recommendations for management of diarrhea

The Common Terminology Criteria for Adverse Events (CTCAE Version 4.0) grading will be used to grade the severity of all AEs and SAEs of diarrhea. Management recommendations for diarrhea are based on the CTCAE grades.

In general, diarrhea should be managed as early as possible after onset of first symptoms with standard antidiarrheal symptomatic treatment, e.g. loperamide.

The medical judgement should be used in decision of the use preventive treatment with loperamide after the first episode of diarrhea.

If diarrhea persists despite optimal symptomatic treatment, treatment interruption (for a maximum of 4 weeks) and dose reduction of nintedanib should be considered based on the recommendations described in [Table 4.2.1.2: 1](#)

Table 4.2.1.2: 1 Recommendations for management of diarrhea

CTCAE Grade	Description	Symptomatic Treatment	Action with study medication
1	Increase of <4 stools per day over baseline	Initiate anti-diarrheal medicines at first signs of symptoms (e.g., 4 mg loperamide followed by 2 mg after each loose stool or every 2-4 hours to a maximum of 16 mg/day  ) until bowel movements cease for 12 hours	Continue same dose of study medication
2	Increase of 4-6 stools per day over baseline	Initiate/continue anti-diarrheal medicines;  If diarrhea grade 2 persists for ≥48-72 hours assess for dehydration and electrolyte imbalance;  In addition, consider IV fluids and electrolyte replacement as clinically indicated.	If diarrhea grade 2 persists for ≥48-72 hours despite optimal symptomatic care:  1. Interrupt study medication until recovery 2. Reduce dose to 100 mg bid after recovery 3. Re-escalate to 150 mg bid if deemed clinically appropriate
3  Or  4	Increase of ≥ 7 stools per day over baseline; incontinence;  Or  Life threatening consequences	Follow recommendations above.  In addition, consider stool work-up to exclude infectious colitis; aggressive IV fluid replacement ≥24 hours, hospitalisation as clinically indicated; consider referral to a GI specialist to rule out potential differential diagnoses.	1. Interrupt study medication until recovery 2. Reduce dose to 100 mg bid after recovery 3. Consider re-escalation to 150 mg bid if deemed clinically appropriate  In case of recurrence of diarrhea grades 3 or 4 despite optimal symptomatic treatment and dose reduction, study medication should be permanently discontinued.

Refer to national prescribing information

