### **Intensity of AEs**

The intensity of the AE should be judged based on the following:

- Mild: Awareness of sign(s) or symptom(s) that is/are easily tolerated  
Moderate: Enough discomfort to cause interference with usual activity  
Severe: Incapacitating or causing inability to work or to perform usual activities

The intensity of **diarrhea adverse events** should in addition be classified and recorded in the (e)CRF according to the Common Terminology Criteria for Adverse Events (CTCAE) version 4 [[R10-4848](#)].

Table 5.3.6.1:1 CTCAE Categorization for diarrhea

CTCAE Grade	
1	Increase of <4 stools per day over baseline
2	Increase of 4 to 6 stools per day over baseline
3	Increase of $\geq 7$ stools per day over baseline; incontinence
4	Life threatening consequences
5	Death

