A2.17	Participation in another trial with investigational drug/s within one month prior to Visit 1 or previous enrollment in this trial	Exclusion criterion 19 met as specified in the protocol Automatic IPV	None

Table 6.2: 1 (continued) Important protocol violations (IPVs)

Category / Code	Description	Requirements / Classification	Excluded from
B	Informed consent		
B1	Informed consent not available/not done	Inclusion criterion 1 not met as specified in the protocol. Automatic IPV	All
B2	Informed consent too late	Inclusion criterion 1 not met as specified in the protocol. Medical review during MQRM, BRPM or DBLM	None
B3	Informed consent not given for pharmacogenetics samples (unspecified part) but blood sample drawn for testing	According to pharmacogenetics database and CRF Automatic IPV	None
B4	Informed consent for pharmacogenetics samples (unspecified part) too late but blood sample drawn for testing	Medical review during MQRM, BRPM or DBLM	None
B5	Informed consent not given for serum banking samples (unspecified part) but blood sample drawn for testing	According to serum banking database and CRF Automatic IPV	None
B6	Informed consent for serum banking samples (unspecified part) too late but blood sample drawn for testing	Medical review during MQRM, BRPM or DBLM	None
C	Trial medication and randomisation		
C1	Incorrect trial medication taken	Wrong medication number use at any time (after Visit 2) during the trial. IPV only if medication error leads to an actual treatment switch (will be determined after unblinding). Medical review of MQRM listings	None
C2	Randomisation not followed	Wrong medication number given leading to the patient taking treatment different from the one randomized by IXRS at time of randomisation (Visit 2). IPV only if medication error leads to an actual treatment switch. (will be determined after unblinding). Medical review of MQRM listings	None
C3	Overall Compliance not between 80% and 120% inclusive	Medical review during MQRM	None
C4	Medication code broken inappropriately	Except for emergency situation. Medical review of MQRM listings	None
C5	Drug not permanently discontinued despite criteria of Section 3.3.4.1 of CTP met	Medical review of MQRM listings	None
D	Concomitant medication		
D1	Patient received prohibited concomitant therapies during treatment phase	Medical review of MQRM listings	None

Table 6.2: 1 (continued) Important protocol violations (IPVs)

Category / Code	Description	Requirements / Classification	Excluded from

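### Section 4.1.4 forbids restart after an undefined severe toxicity, while the diarrhea table (first grade 3 or 4 episode) and Section 4.2.1.1 (other related AEs) allow it, and no text says which prevails

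*Protocol*

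**What the plan says.** Four protocol texts and one SAP line bear on when treatment ends for good.

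- **Protocol 4.1.4, Drug administration.** "In the case of severe toxicity or when the reduced dose is again not tolerated, drug treatment must be stopped and cannot be restarted". The sentence has two triggers joined by an or: severe toxicity at any dose, and renewed intolerance at the reduced dose. It carries no cross-reference and no exception.
- **Protocol 4.2.1.2, Table 4.2.1.2:1, grade 3 or 4 row.** Grade 4 is described as "Life threatening consequences". The action is to interrupt until recovery, resume at the reduced dose, then "Consider re-escalation to 150 mg bid if deemed clinically appropriate". The permanent stop comes later: "In case of recurrence of diarrhea grades 3 or 4 despite optimal symptomatic treatment and dose reduction, study medication should be permanently discontinued".
- **Protocol 4.2.1.1, other adverse events.** "After resolution of AE, nintedanib may be reintroduced and re-escalated to the higher dose (at the discretion of the investigator". The text sets no upper limit on severity. Its heading excludes diarrhea and liver enzyme elevations.
- **Protocol 3.3.4.1, removal of individual patients.** A third formulation: withdrawal for toxicity judged unacceptable even after dose adjustment and supportive care, alongside listed events such as hepatic injury.
- **SAP 6.2, Table 6.2:1, code C5.** The violation is defined as "Drug not permanently discontinued despite criteria of Section 3.3.4.1 of CTP met". It names no other section.

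**The concern.** A stopping rule has to give the same answer wherever a site reads it. Here a mandatory sentence rules out restart, while a table written for the drug's most frequent adverse event (diarrhea, per Section 1.2) describes how to restart after a first severe episode, including a life-threatening one. Two investigators with the same patient could each comply and do opposite things.

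The first stake is patient safety. The second is interpretability: summaries of discontinuation, dose reduction and exposure would partly reflect which section a site consulted. A monitor could not say whether a restart after a severe event is a protocol violation. There is also a limited link to efficacy. SAP Table 6.1:1 cuts the efficacy data at the day after last drug intake, so the stopping decision affects which measurements count.

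**Working it through.** The point rests on a comparison of texts; there is no plan figure to reproduce. Taking each clinical situation in turn:

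| Situation | Section 4.1.4 | Specific section | Result |
|---|---|---|---|
| First grade 4 diarrhea | Severe toxicity on any ordinary reading: stop, no restart | Table 4.2.1.2:1: interrupt, resume at reduced dose, consider re-escalation | Conflict |
| First grade 3 diarrhea | Stop, no restart, if grade 3 counts as severe toxicity | Same row as grade 4 | Conflict depends on the undefined term |
| Recurrent grade 3 or 4 despite symptomatic treatment and dose reduction | Stop | Table 4.2.1.2:1: permanent discontinuation | Agree |
| Grade 1 or 2 diarrhea | Severe-toxicity trigger not met | Continue, or interrupt and reduce | No conflict on this trigger |
| Severe related event, neither diarrhea nor liver enzyme elevation, not listed in 3.3.4.1 | Stop, no restart, if it counts as severe toxicity | 4.2.1.1: reintroduction and re-escalation at investigator discretion | Conflict |

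**What severe toxicity could mean.** The protocol's definition of severe is in the AE intensity scale of Section 5.3.6.1: "Severe: Incapacitating or causing inability to work or to perform usual activities". Section 4.1.4 does not refer to it. Section 5.3.6.1 has diarrhea classified by CTCAE grade in addition to intensity, so the two scales run in parallel and nothing maps one to the other. A site could therefore hold that grade 3 diarrhea is not severe toxicity. That is hard to hold for a life-threatening event.

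**What C5 covers.** Section 3.3.4.1 repeats almost all of the hepatic-injury list behind the permanent stop in Table 4.2.1.3:1, so C5 reaches those cases. Its item on toxicity despite dose adjustment plausibly covers recurrent grade 3 or 4 diarrhea and failure at the reduced dose. Two kinds of stop are not clearly listed there: the stand-alone severe-toxicity stop in 4.1.4, and the stops in Table 4.2.1.3:1 for AST/ALT that stay at or above 3 x ULN or return to that level.

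**Illustrative size.** The documents give no rate of grade 3 or 4 diarrhea; Section 1.2 says only that the vast majority of cases were mild to moderate. Assume 2% to 5% of the approximately 350 randomised patients have such an episode:

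- 350 x 0.02 = 7
- 350 x 0.05 = 17.5, rounded to 18

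This assumes that all 350 start nintedanib and that every grade 3 episode counts as severe toxicity. It leaves out other severe related events, for which no rate is given.

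**The case against.** The strongest reply is that the protocol repeatedly sends sites to Section 4.2 or 4.2.1 for dose management: Sections 3.1, 4.1 and 4.1.3 do so, and 4.1.4 itself refers there for temporary discontinuation, dose reduction and re-escalation. A site would then use the specific table. This shows where sites are likely to look, but none of these references qualifies the sentence that forbids restart. The converse reply, that 4.2.1 contains only recommendations and the mandatory sentence prevails, leaves the table describing a restart that the protocol prohibits. Neither order of precedence is written down.

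The objection that severe toxicity is undefined stands in part. It makes grade 3 a matter of interpretation rather than a proven contradiction. It does not dispose of grade 4.

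Three stronger readings are tempting and should not be made.

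- A reader might infer that 4.2.1.1 is a further opposing rule for diarrhea. Its heading takes diarrhea out of its scope, so it conflicts with 4.1.4 only for other severe related events.
- A reader might infer a contradiction for grade 2 diarrhea, because that row states no stop for a patient who fails again at the reduced dose. That is silence, which 4.1.4 and 3.3.4.1 can fill.
- A reader might infer that C5 misses every permanent stop in the tables. As shown above, 3.3.4.1 already covers the hepatic-injury stops and plausibly repeat toxicity. C5 also excludes patients from no analysis set, and Protocol Section 7.3 has no per-protocol set, so the gap affects the listing of violations and not the analysis populations.

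**Conclusion.** The concern holds as a conflict between sections on restart after a severe event. It is clear for a first grade 4 diarrhea. For a first grade 3 diarrhea it depends on the meaning of severe toxicity. It is also present, subject to the same term, for severe related events that fall under 4.2.1.1. Section 3.3.4.1 adds a third wording that does not settle the matter.

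The number of patients affected cannot be derived from the documents. The 7 to 18 of 350 shows scale under an assumed rate and should not be cited as an estimate. The finding does not depend on it, since one such patient is enough for two compliant sites to diverge. The effect on analysis is secondary: no endpoint definition or analysis set changes, but stopping dates feed the efficacy data cut-off and the safety summaries. The case for correction rests mainly on safety and consistent conduct.

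**What to change.** 1. Reconcile Protocol Sections 3.3.4.1, 4.1.4, 4.2.1.1 and 4.2.1.2 so that a single rule states which events end treatment permanently and which allow restart. The choice of rule belongs to the sponsor's medical team; no view is offered here.
2. Define severe toxicity by reference to a named scale, or replace the term.
3. Have 4.1.4 point to the reconciled rule instead of stating its own.
4. Align SAP code C5 with that rule and with the permanent stops not clearly listed in 3.3.4.1, namely the severe-toxicity stop of 4.1.4 (in whatever form survives) and the AST/ALT persistence or recurrence stops in Table 4.2.1.3:1.

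The cost is protocol wording, a letter to sites and one line in the SAP violation table. No new data, visits or sample size are needed.
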